Identifiers: NCT04072549 Unique Protocol ID: Pro00086238

Brief Title: Reducing Health Disparities in Childhood Obesity

Date: Jan 22nd, 2026

Methods

This randomized controlled trial was conducted during summer 2021, 2022, and 2023. The study followed the Consolidated Standards of Reporting Trials (CONSORT) reporting guidelines. All procedures were approved by the Institutional Review Board of the University of South Carolina and the study was preregistered at Clinicaltrials.gov (NCT04072549).

Study Design and Participants.

We partnered with 7 Title I elementary schools from a single school district in a mid-sized metropolitan city in the southeastern United States that served 2,904 children from low-income families across the 3 years of the study. The average poverty rate at our partnering schools was 74% of the student population. In the spring (March-April) of each school year, we sent invitations to parents of children enrolled in kindergarten through 4th grade via each school's social worker, paper flyers, and electronic communications (i.e., online newsletter and Class Dojo). Recruitment materials were available in both English and Spanish. Children were eligible to participate if they were enrolled in one of our partner Title I schools, did not anticipate moving during the summer, and were able to complete the measures during the spring and summer (e.g., not out-of-state visiting relatives during the entire summer). Informed consent was obtained from one parent and/or guardian through an online Health Insurance Portability and Accountability Act (HIPAA)-compliant web-based survey platform accessed via a smartphone.

Randomization and Blinding.

Once parents completed the informed consent which confirmed their participation in the study and income proxy screener (i.e., public assistance services utilized and parent education), children were randomly allocated at a 1:1 ratio to either control (i.e., summer as usual) or intervention (i.e., free SDC), stratified by public assistance services used/received within family units, grade, and gender. Where parents had two or more eligible children, siblings were grouped together to ensure siblings were randomized to the same condition. Children were allowed to participate in the study for a single summer. Randomization occurred prior to baseline assessments each May. The decision to randomize at this time was made to treat the participating families with dignity and be respectful of their needs in making alternative summer care arrangements if their child was not randomized to receive free SDC. Randomization was performed by a co-investigator ([name]) external to the day-to-day conduct of the trial using a stratified random number generator in STATA (StataCorp LLC, v.18.0). The lead investigator ([name]) and data collectors were blinded to allocation.

Intervention and Control Conditions.

The intervention group was randomly assigned to receive 8 to 10 weeks of free SDC. The difference in the number of weeks was due to summer 2021 being shorter than summers 2022 and 2023 because of COVID-19 school closures. The SDC that served as the intervention was operated by a local parks and recreation commission, which operated multiple summer programs across the school district. The SDC provided indoor and outdoor opportunities for children to be physically active each day, included enrichment and academic programming, weekly field trips, and provided breakfast, lunch, and snacks. The foods served adhered to existing federal food program nutrition guidelines by the USDA and were reimbursed via the Summer Food Service Program (<https://www.fns.usda.gov/summer/sunmeals>). The SDC maintained a ratio of 1 staff member for every 12 children enrolled – consistent with childcare regulations. The SDC operated daily (Mon-Fri) for 8 to 10 weeks during the summer (except for the 4th of July holiday week). The SDC opened at 7am for morning drop-off and ended at 5pm each day. Based on the schedules of the SDC, physical activity opportunities were scheduled for 3 to 4 hours each day, with the remaining 4 to 5 hours dedicated to enrichment/academic content or field trips. An example menu and daily schedule are provided in Supplemental eFigure 1. The local parks and recreation commission had a history of operating SDCs in the community and had the appropriate safety and staff training certifications to ensure a safe/nurturing environment. Each summer a single SDC was provided for children to attend. The SDCs operated according to routine practice, with no outside assistance or modifications from the investigative team. In summer 2022 and 2023, the school district provided transportation for children assigned to the intervention group. No transportation was provided in 2021 due to COVID-19. The control group did not receive free SDC programming. These children experienced what we consider “summer as usual” (see Summer Programming Exposure below).

Measures

BMI z-score.

The primary outcome was change in age-sex specific BMI z-scores. Height (cm) and weight (kg) without shoes and excess clothing (e.g., jackets) were measured in triplicate as close to the end of the school year (right before summer vacation) in May and again upon return from summer at the start of the school year in mid-August. All measures were collected using research-grade stadiometer (HM 200P Portstad, Charder Eletcri Company, Ltd, Taiwan) and a digital scale (Digital Scale, MAXUS, China) by physical education teachers and trained research staff. Data collectors did not have any knowledge of group assignment when conducting the height and weight assessments. The original study was designed to assess BMI at the beginning of the school year (i.e., fall, August), the end of school year (i.e., spring, May), and again at the start of the next school year (i.e., fall, August). Unfortunately, the COVID-19 pandemic disrupted this timeline for 2021 where we had to forgo the three timepoints and only collect before (i.e., spring, May) and after summer (i.e., fall, August) BMI measures. Thus, what is present in this paper are the before summer and end of summer measurements of BMI.

Physical Activity and Sedentary Behaviors. Physical activity (PA) and time spent sedentary were measured using a wrist-placed accelerometry (ActiGraph GT9X) on the non-dominant wrist with a 24-hours wear protocol for 14-days.^{1,2} The ActiGraph GT9X accelerometer is a triaxial research-grade accelerometer frequently used in studies measuring children's free-living 24-hour behaviors (i.e., PA, sedentary behavior, sleep). ActiGraph GT9X accelerometers were initialized and downloaded using Actilife software (version 6.13.4, ActiGraph LLC). Accelerometers were initialized to record data at a frequency of 30 Hz. Stop time was not used. Idle sleep mode was enabled to preserve battery life and the display was turned off to limit distractions for children while attending school.

Assessment of PA behaviors were collected at two timepoints each year – during school (April/May, average daylight 13hrs) and again during summer (mid-July, average daylight 14hrs). Children were instructed to wear the device during school and summer for 14 consecutive days during each assessment period. Devices were distributed and returned by mail. Each mailing contained a device and information regarding wear procedures (e.g., wear while awake and sleeping, waterproof). Data were downloaded and saved in raw format as .gt3x files and were processed using the GGIR package (version 2.8-2) in R (Version 4.1.2; R Foundation for Statistical Computing; Vienna, Austria). Time spent in PA intensity categories was determined using intensity thresholds described by Hildebrand et al.^{3,4} A valid wear day was defined as a minimum of 16 hours and participants were included if they had at least one day of data.⁵ The primary metrics of interest were time spent in MPVA and time spent sedentary in minutes per day.

Sleep. The amount of time (minutes per day) a child sleeps was collected via the wrist-placed ActiGraph on the non-dominant hand (described above).⁶⁻⁸ This procedure has been validated as a measure of sleep and is used extensively in studies evaluating sleep.⁷⁻¹¹ The amount of time a child sleeps each night will was determined using two methods that are widely used in the sleep literature with children: 1) ActiGraph proprietary sleep algorithms to determine time spent sleeping, and 2) cross-referencing with parental/guardian report of time in bed and time of wake from the daily logbook.

Screen Time. Each evening of the 14-day accelerometer protocol, parents received a text via their smartphone to complete a time use record (see “Structured Program Exposure – Time Use Record” section below for details). One of the questions of the time use record asked parents to estimate the total amount of time (hours and minutes) their child spent in front of a screen that day (e.g., TV, computer, video game, smartphone, and tablet).

Food and Beverage Consumption. Children's food/beverage consumption was obtained via parent-reported daily diaries for 14 days during the spring (April/May) and 14 days during summer (July). Weekend days were excluded in analyses as the intervention was only delivered on weekdays. Within the daily diaries, parents completed a modified version of the 2009-2010 National Health and Nutritional Examination Survey (NHANES) Dietary Screener Questionnaire (DSQ).¹² The DSQ is a 26-item food frequency questionnaire in which parents report the frequency of foods/beverages consumed by their child each day, including fruits and vegetables, dairy/calcium, sugar-sweetened beverages, sweets/desserts, whole grains, red meat, and processed meat. For this study, questions on meat were excluded as there is no strong association between meat consumption and childhood obesity, while a question around snacks/chips was added to best reflect the diet of children.¹³ Parents

were sent the daily diary at 8:00pm each day and were asked to complete this with their child to report on what their child ate and/or drank that day. Unlike the original screener, which asked respondents about consumption over the past 30 days (e.g., 1 time last month, 2 times per week), only response options referring to the frequency of consumption for that day were included (e.g., 1 time today, 2-3 times today) to capture day to day variation in consumption of each food/beverage component. For foods items, response options were “none”, “1 time per day”, and “2 or more times per day”. For beverages, the response options were “none”, “1 time per day”, “2-3 times per day”, “4-5 times per day”, and “6 or more times per day”. Procedures for assessing daily food/beverage consumption used in this study were similar to previous investigations with similar populations.¹³ During analysis, response options were collapsed and recoded as did eat/consumed or did not eat/did not consume.

Child and Parent Demographics.

Each spring (April/May) parents completed a brief survey via their smartphone to collect information about the child (e.g., biological sex, parent self-identified race/ethnicity), household income, parent highest education level obtained, household food insecurity status, and the use/receipt of any of the following services: Welfare, Temporary Assistance for Needy Families (TANF), Temporary Cash Assistance (TCA), Children's Health Insurance Program (CHIP), Medicaid, Supplemental Nutrition Assistance Program (SNAP), Women, Infants and Children (WIC), or Supplemental Security Income (SSI).

Summer Programming Exposure.

We recognized that children randomized to the control condition (i.e., summer as usual) could voluntarily elect to enroll in some type of summer programming. Based on national data, we anticipated approximately 20% of the children randomized to the control would attend some type of summer programming.¹⁴ Conversely, we recognized children randomized to receive free SDC could elect to not attend the free SDC or attend some other summer program offered. To account for differential exposure to summer programming in both the control and intervention groups, we collected information regarding summer programming attendance in three ways. First, at the beginning of summer (early June), parents completed a brief survey on their smartphone of the types of summer programming their child was anticipated to enroll in. Parents indicated the anticipated number of weeks enrolled in a program, the number of days per week the child was anticipated to attend, and whether the program was whole or half day. Second, on Friday of each week of the summer, parents received a text with a link to a brief survey about their child's attendance in a summer program for that week. Parents indicated if their child attended a summer program that week and, if yes, on what days of the week they attended, and for how long each day. Third, during a 14-day period in mid-July, parents were texted each evening at 9PM and asked to complete a daily time use record. Each record took ~7min to complete. Parents indicated the places/locations their child went during the day and the times they were there. Completed time use records for weekdays (the days when a child could attend a summer program) were used to estimate summer program exposure.

Statistical Power.

Sample size calculations were based on the ability to detect a statistically significant group (intervention vs control) by time (before summer to end of summer) difference in the change in zBMI with a mixed-effects model with statistical power of 0.80 and an alpha of 0.05. Estimates from the largest and most recent studies¹⁵⁻¹⁷ conducted to date reported the average change in zBMI during the summer ranged from 0.04 to 0.09, and the average change in zBMI during the school year was -0.02. Accounting for the intraclass correlation at the school level¹⁸ and an anticipated attrition rate of 25%, the total number of children required to be enrolled at baseline was 420 to arrive at a final sample of 330 (165 per condition).

Statistical Analyses.

BMI. The primary analysis was intent-to-treat (ITT), defined as using all available data from children according to the original group they were randomized (free summer day camp or continue summer as usual) regardless of their attendance at a summer program. Analyses used mixed-effects models, accounting for the nesting of repeated measures within children, families (i.e., siblings), and schools. The treatment effect of interest was the group (intervention vs control) and time (pre summer vs post summer) interaction. Missing data on the primary outcome (zBMI) was accounted for using full information maximum likelihood estimation, allowing for all children's zBMI data to be used regardless of missing zBMI at either pre or post summer. Covariates included in

the model were the child's baseline zBMI, biological sex¹⁹ and age,²⁰ self-reported race/ethnicity,²¹ parent education,²² food insecurity status,²³ and poverty level.²⁴ Missing data on covariates were handled using multivariate multiple imputation of 100 datasets for both continuous and categorical covariates using STATA v18.0 multiple imputation commands. Secondary analyses examined the dose-response of summer program attendance including both the intervention and control groups. These models used each of the three summer program exposure metrics as continuous independent variables (standardized to the percentage of days attended during the week), to examine the impact of the amount of summer programming on changes in zBMI. The assumptions for all models were checked using plots of the estimated residuals, no violations were found.

MVPA, Screen Time, Sleep. The primary analysis was intent-to-treat (ITT), defined as using all available data from children according to the original group they were randomized (free summer day camp or summer as usual) regardless of their attendance at a summer program (e.g., intervention children never attending the SDC and control children attending some other form of SDC). Analyses used mixed-effects models, accounting for the nesting of repeated measures within children, families, and schools. The treatment effect of interest was the group (intervention vs control) and time (pre summer vs post summer) interaction. Missing data on the dependent variables of interest of MVPA, time spent sedentary, sleep, and screen time were accounted for using full information maximum likelihood estimation,²⁵ allowing for all children's data to be used regardless of missing data at either pre or post summer. Covariates included in the model were the child's biological sex¹⁹ and age,²⁰ self-reported race/ethnicity,²¹ parent education,²² food insecurity status,²³ and poverty level.²⁴ Missing data on covariates were handled using multivariate multiple imputation with the covariates serving as variables to inform the imputation of 100 datasets for both continuous and categorical covariates using STATA v18.0 multiple imputation commands.

Secondary analyses (i.e., exposure models) examined the exposure to structured programming and included both the intervention and control groups. For these analyses we defined exposure to structure as any day where a child is reported on the TUR to have attended a structured setting outside the home (attended/not attend, binary variable). This choice of dichotomizing structured settings at the day level was done because the distribution of minutes in a structured setting was heavily skewed in the summer. Children (both intervention and control), when they were reported to have attended a structured setting in the summer, did so for a day-long program (i.e., 7-8hrs), which for the intervention group was the typical length of attending the SDC. This means that for the children in the control group, when they did attend structured programming in the summer, this programming lasted for approximately the same length of time as the intervention group. Because all children were exposed to school, exposure to structured programming during school (April/May) excluded attending school and, therefore, represents only additional structured programming a child was exposed to above and beyond the school day. In addition to changes in the continuous outcomes, we examined the probability of meeting MVPA (≥ 60 minutes per day) and screen time (≤ 120 minutes per day) guidelines²⁶ using both the above stated ITT and exposure to structured programming models. All models included both weekdays and weekend days. Because free SDC was provided on weekdays only, we also conducted the same ITT and exposure analysis restricting the data to only weekdays. The assumptions for all models (normality of residuals, homoscedasticity) were checked using; no violations were found. All models were conducted using STATA v18.0 (College Station, Texas).

Diet. The primary analysis was intent-to-treat (ITT), defined as using all available data from children according to the original group they were randomized to (free SDC or summer as usual) regardless of their parent-reported attendance at a summer program.²⁷ Mixed effects models were used to account for the nesting of repeated daily measures within children. The analyses examined the odds of consuming different foods/beverages during weekdays in the summer, controlling for school year endorsement of consuming that food or beverage, in the free SDC group compared to summer as usual. During analysis, day-level food/beverage response options (e.g., 1 time today, 2-3 times today) were collapsed and recoded as binary values: 1 = consumed and 0 = did not consume. Analyses excluded weekend days as the intervention was only delivered on weekdays. Missing data for outcome variables were accounted for using full information maximum likelihood estimation, allowing for all children's data to be used regardless of missing data. Covariates included child biological sex, parent education, food security status, the use of assistance services (e.g., SNAP, WIC), and income. Missing data for covariates was handled using multiple imputation of 100 datasets for both continuous and categorical covariates.

Secondary analyses were as-treated, defined as using all available data from children based on their parent-reported attendance at a structured program on weekdays in the summer, regardless of what group they were randomly assigned to.²⁸ This analysis examined the impact of attending structured summer programming, both

as a binary predictor (days children attended vs days not attended) and as categorical minutes attended (30-239min/d or ≥ 240 min/d vs did not attend “zero” minutes [reference group]) on the odds of consuming different food/beverages during weekdays in the summer, controlling for consumption during the school year and all covariates included in the primary analysis. The 30-239min/d grouping corresponds to half-day or shorter programs, while ≥ 240 min/d corresponds to longer than half-day up to full-day programs. The assumptions for all models were evaluated by examining multicollinearity, residual plots, and the distribution of random effects; no violations were found. STATAv17.0 was used to run all statistical analyses

References

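### The models do not name all the factors used in randomisation, and none includes summer; the likely cost is a slightly conservative test and a small loss of precision

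*Combined protocol and SAP*

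**What the plan says.** Under Randomization and Blinding, "children were randomly allocated at a 1:1 ratio", "stratified by public assistance services used/received within family units, grade, and gender". The same section adds that "Randomization occurred prior to baseline assessments each May" and that "Children were allowed to participate in the study for a single summer". Each summer is therefore a separate round of randomisation with its own children, and summer is a between-child factor.

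The covariates under Statistical Analyses are:

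- **BMI (primary outcome).** Starting zBMI, sex, age, race or ethnicity, the parent's education, food insecurity and poverty level. Nesting is in child, family and school.
- **MVPA, Screen Time, Sleep.** The list opens "Covariates included in the model were the child's biological sex" and continues as for BMI, without a starting value. Nesting is the same.
- **Diet.** "Covariates included child biological sex, parent education, food security status, the use of assistance services (e.g., SNAP, WIC), and income". Nesting is in child only.

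Poverty level is not defined. None of the three sections gives summer a fixed effect, a stratum or a random level.

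Intervention and Control Conditions says that summer 2021 was shorter than the other two and had no transport, whereas "In summer 2022 and 2023, the school district provided transportation for children assigned to the intervention group". It also says that "Each summer a single SDC was provided for children to attend".

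**The concern.** Restricting randomisation by a factor removes chance imbalance on that factor, so the treatment estimate varies less from trial to trial than simple randomisation would allow. A model without the factor does not credit this. Its standard error is too large and its test rejects too seldom under the null. Summer works in the same way, because children were allocated separately each year.

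Summer also deserves attention for itself. A shorter summer could alter change in both arms, and lack of transport could alter attendance in the intervention arm. A single pooled effect, with no summer term and no result by year, cannot show whether 2021 behaved differently. The BMI section handles missing zBMI by full information maximum likelihood, which relies on missingness being at random given what is in the model. If loss by arm varied between summers and change did too, a model without summer would not meet that condition.

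**Working it through.** **1. Factors used in randomisation against terms in the models**

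| Factor | BMI | MVPA, screen, sleep | Diet |
|---|---|---|---|
| Public assistance | not named; poverty level undefined | not named; poverty level undefined | included |
| Grade | not named; age is a close proxy | not named; age is a close proxy | neither grade nor age |
| Gender | sex | sex | sex |
| Summer | absent | absent | absent |

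**2. The plan's own sample size as a base**

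Statistical Power gives 330 children analysed (165 per condition), power 0.80 and alpha 0.05, taken here as two-sided. The 330 cannot be rebuilt, because no SD, target difference or intraclass correlation value is stated. (Separately, 330/(1 − 0.25) = 440, not the stated 420; that does not bear on this point.) Ignoring clustering, 165 per arm detects

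(1.960 + 0.842) × √(2/165) = 0.308 SD of change.

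**3. Effect of omitting balanced factors in a linear model**

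Let R² be the share of the variance of change that the omitted factors explain beyond the covariates already present. The documents give no value, so R² is an assumption. At the planned effect, effect/SE = 2.802. Then:

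- SE factor if adjusted = √(1 − R²)
- true type I error if omitted = 2 × [1 − Φ(1.96/√(1 − R²))]
- power if omitted = Φ((2.802 − 1.96)/√(1 − R²))
- power if adjusted = Φ(2.802/√(1 − R²) − 1.96)

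| R² | SE factor | Type I error, omitted | Power, omitted | Power, adjusted | Difference (points) |
|---|---|---|---|---|---|
| 0.01 | 0.995 | 0.049 | 80.1% | 80.4% | 0.3 |
| 0.05 | 0.975 | 0.044 | 80.6% | 82.0% | 1.4 |
| 0.10 | 0.949 | 0.039 | 81.3% | 84.0% | 2.7 |

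A simulation of 4,000 trials per setting (330 children, three equal summers, stratified allocation, complete data, no sibling or school clustering) agreed. At R² = 0.10, type I error was 0.040 omitted and 0.052 adjusted; power was 80.6% and 83.8%.

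**4. Which R² is plausible for summer alone?**

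As an illustration, suppose that one of three equal summers differs by 0.05 zBMI in mean change. The between-summer variance is 0.05² × (1/3) × (2/3) = 0.00056. Taking a contrast of 0.04 − (−0.02) = 0.06 as the detectable difference implies an SD of 0.06/0.308 = 0.195. Then R² = 0.00056/0.195² ≈ 0.015, and the SE would fall by about 0.7%. This points to the lower end of the table.

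**5. The form in which the terms enter**

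The tested term in the BMI and activity models is group by time. In one simulated complete-data mixed model (R² = 0.20), adding summer and strata as main effects left the estimate at 0.2103 and its SE at 0.1155. Adding their interactions with time cut the SE to 0.1017. Main effects describe level; only the interactions explain change.

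**6. What a result by summer could show**

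If summers were equal in size, 330/3 = 110 children, or 55 per arm. The detectable difference within one summer is (1.960 + 0.842) × √(2/55) = 0.53 SD.

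**The case against.** Several counter-arguments have force.

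- **Poverty level may already be the stratum.** Randomization and Blinding treats public assistance as part of an income proxy, so poverty level may stand in for it, at least in part. This stands as an ambiguity. It does not settle the matter: Child and Parent Demographics collects income and receipt of services separately, and the diet model enters both. A reader might infer that public assistance is certainly missing from the BMI and activity models; the documents show only that it is not named.
- **The gain is small.** This stands. zBMI is already standardised for age and sex, and the models carry several socioeconomic covariates, so the added R² may be low. The table also applies only to linear models. In the binary models (diet, and meeting the activity and screen guidelines), adjustment changes the conditional odds ratio and need not shrink its SE.
- **Main effects would do nothing.** This is correct for the group-by-time models, and is why the remedy must specify interactions or ANCOVA.
- **The analyses are complete.** The text reports model checks as already done, so a respecified primary model would be post hoc. This stands and limits the request to a sensitivity analysis.

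A reader might also infer that each summer delivered a different intervention, or that the results belong to three distinct camps. The documents do not support this. Only 2021 is described as different, in length and transport; no difference between 2022 and 2023 is stated. The operator and its routine practice are described in common for all summers, and nothing says whether the site changed.

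**Conclusion.** The gap is real and modest. No model accounts for summer, the diet model lacks grade and age, and the BMI and activity models do not name public assistance. With balanced strata and an assumed added R² of 0.01 to 0.10, the linear-model tests run at a true type I error of 0.049 to 0.039, and power is about 0.3 to 3 points lower than it could be. These figures assume 330 analysed, a two-sided test and no clustering.

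A reader might infer that the treatment effect is biased or that false positives are inflated. Neither follows. The direction is conservative while 1:1 allocation held within each summer and losses were similar by arm across summers. Bias would need one of these to fail, together with a between-summer difference in change. The documents give no data on any of these, and the published 0.04 to 0.09 range of summer change is a range across studies, not across years of this trial. The bias therefore cannot be sized here.

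**What to change.** - State how poverty level is defined and whether it is the public-assistance stratum. If it is not, add that stratum to the BMI and the MVPA, screen-time and sleep models.
- Add summer (three levels) to all models, and grade or age to the diet model.
- In the group-by-time models, enter summer and the stratification factors with a time interaction, or use an ANCOVA form. In the diet model, which compares summer days given school-year consumption, main effects are enough.
- Report the group effect by summer, at least 2021 against 2022 and 2023 combined, as descriptive only, given the low power within a summer.
- Present the refit as a labelled sensitivity analysis beside the reported one. A table of numbers randomised and analysed by arm and summer would show whether the conditions for bias arise.

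The cost is a few extra model terms and a refit; every variable is already collected.

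### In the secondary zBMI dose-response models, plans stated in June are analysed as days attended, so that one slope is biased as an estimate of the attendance effect

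*Combined protocol and SAP*

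**What the plan says.** Under Summer Programming Exposure, the combined protocol and SAP explains why exposure is recorded at all. Control children may find a programme of their own (about 20% are expected to), and "children randomized to receive free SDC could elect to not attend the free SDC". Three sources follow:

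- **Early June.** "parents completed a brief survey on their smartphone of the types of summer programming their child was anticipated to enroll in". The dose items are forecasts too: "Parents indicated the anticipated number of weeks enrolled in a program, the number of days per week the child was anticipated to attend", together with whole or half day.
- **Every Friday of the summer.** A texted survey on the week just ended: "Parents indicated if their child attended a summer program that week and, if yes, on what days of the week they attended".
- **Fourteen days in mid-July.** A daily record of places and times: "Completed time use records for weekdays (the days when a child could attend a summer program) were used to estimate summer program exposure".

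The BMI paragraph of Statistical Analyses then describes a secondary analysis of dose-response to attendance in both arms: "These models used each of the three summer program exposure metrics as continuous independent variables (standardized to the percentage of days attended during the week".

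No section relabels the June measure as planned dose, corrects it for later non-attendance, or says which of the three measures leads. The paragraph on MVPA, screen time and sleep again mentions, in its definition of ITT, intervention children who never go to the camp.

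**The concern.** The models are meant to show how the change in zBMI depends on the amount of programming a child received. Two of the three measures report what happened. The June measure reports what a parent expected, yet it is put on the same scale and interpreted in the same way. The plan collects exposure data because expectation and attendance can part company, and this measure cannot see that gap. A child with a full summer planned in June who never appeared carries a full dose.

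The consequence is that one of three slopes presented as dose-response to attendance answers a different question, about planned dose. If it differs from the other two, the plan gives no rule for which one describes attendance.

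**Working it through.** The plan states no figure for planned against actual attendance, so there is nothing to reproduce. The check is how a slope on planned dose relates to the slope on attendance.

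**Inputs**

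- From the documents: the June measure holds anticipated weeks and days; all three measures enter as continuous percentages of days; non-attendance is foreseen without a number; about 20% of controls are expected to attend something.
- Assumed: q, the share of children with planned attendance who never attend; u, the share without a plan who do attend; a true slope of -0.09 zBMI per 100% of days; a residual SD of 0.3. In the simulations all intervention families and 20% of control families plan to attend.

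**Formula.** Let A be planned dose, D attended dose, and Y = βD + e with e unrelated to A. The slope of Y on A is β × cov(D, A) / var(A). For all-or-none plans this is β × [mean D among planners − mean D among non-planners] = β × (1 − q − u).

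**All-or-none plans, u = 0**

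| q | 1 − q | Simulated ratio to β (n = 400,000) |
|---|---|---|
| 10% | 0.90 | 0.93 |
| 20% | 0.80 | 0.81 |
| 30% | 0.70 | 0.69 |
| 50% | 0.50 | 0.52 |

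With u = 20% and q = 30% the ratio is 1 − 0.30 − 0.20 = 0.50 (simulated 0.51). With actual attendance as the exposure, the simulated ratio was 0.97 to 1.04 for every q and u tried.

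**Graded plans.** The June survey is graded, not all-or-none. If no-shows are random with respect to the planned amount, mean D given A is (1 − q) × A, so the ratio is again 1 − q. Simulated ratios were 0.91, 0.80, 0.71 and 0.49 at the same four values of q.

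**Could the errors average out?** Not at the ends of the scale. A child planned at 100% can only attend less, and a child planned at 0% can only attend more. Both shrink the contrast.

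**No-shows related to outcome.** Take q = 30%, u = 0, and let no-shows differ in zBMI change by ±0.05. The slope on A is β(1 − q) + shift × q.

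- Shift +0.05: −0.063 + 0.015 = −0.048, a ratio of 0.53 (simulated 0.54).
- Shift −0.05: −0.063 − 0.015 = −0.078, a ratio of 0.87 (simulated 0.88).

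In the same two scenarios the slope on actual attendance was 1.18 and 0.84 times β. Using attendance cures the miscoding but not self-selection.

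**Coverage of the two attendance measures.** Fourteen days hold 10 weekdays. The camp ran 8-10 weeks, or 40-50 weekdays, so the July record covers 10/50 to 10/40 = 20-25% of them. If the closed 4 July week lies inside that count, the denominator is 35-45 and the share 22-29%. The Friday survey runs through the whole summer.

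**The case against.** The reach is narrow. One of three measures is affected, in a secondary analysis. The primary zBMI analysis compares randomised groups and uses no exposure measure. The exposure models for activity, screen time and sleep use the time use record, and the as-treated diet analysis uses parent-reported attendance. All of this stands.

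The plan openly calls the June items anticipated, and showing several imperfect measures side by side is a common robustness approach. The disclosure is real, but the analysis paragraph removes the distinction by scaling all three as days attended. Measures in a robustness set should also target the same quantity; planned and received dose do not.

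A reader might infer that every child who never attended is counted as exposed. The text supports this only where the parent anticipated attendance in June; a never-attender with no plan is coded zero. A reader might also infer that the June measure merely repeats the randomised arm, since the camp was free and allocation came before June. The documents give no enrolment plans by arm, so this is conjecture. If it were true, the June measure would be less open to self-selection after randomisation than attendance is, which is a reason to keep its model under an honest label.

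Finally, the document is dated January 2026, covers the summers of 2021 to 2023 and reports that model assumptions were checked. The models therefore appear to have been run, and deleting one now could look like selective reporting. That objection stands and shapes the remedy.

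**Conclusion.** The point holds in a limited form. In the secondary zBMI dose-response analysis, a forecast is treated as received dose, and the resulting slope is biased as an estimate of the attendance effect. The direction is toward zero if non-attendance is unrelated to outcome.

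The 0.5-0.9 range is not an estimate for this trial and not a bound. It rests on assumed no-show rates of 50% to 10%, all-or-none plans, no unplanned attendance and uninformative no-shows. Unplanned attendance would lower the ratio further, and outcome-related no-shows would move it either way.

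It would be tempting to conclude that the dose-response findings as a whole, or the trial's main result, are wrong. The documents do not support that: the Friday and July measures record reported attendance, and the ITT comparison does not depend on exposure. Nor do they show that the three slopes conflict.

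**What to change.** - Base the attendance dose-response on reported attendance. Make the Friday survey the main dose, because it is the only record of reported attendance across the whole summer.
- Count weeks reported as not attended as zero. Treat weeks with no survey answer as missing, so that non-response does not become zero dose.
- Keep the mid-July time use record as a check.
- Keep the June model, but describe it only as planned (anticipated) dose.
- Tabulate planned against reported attendance by arm, which would supply the figures now missing.
- State that the main measure was chosen after the models had been run, if that is so, and report all three slopes.

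The cost is a few sentences, one table and a missing-week rule, with no new data; the weekly model may need refitting if unanswered weeks were handled differently. The drawback is that the choice of main measure is post hoc, which disclosure limits but does not remove.
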